10.2. Populations for Analyses

For purposes of analysis, the following populations are defined:

Population	Description
All Participants Enrolled (APE) Population	All participants who are screened for eligibility
Modified Intent-to-Treat (MITT)	All randomized participants who receive at least one dose of study treatment. Participants will be analyzed according to the treatment that they were randomised to. The MITT Population will be used for all efficacy summaries.
Per-Protocol (PP) Population	The PP population is comprised of the MITT population, excluding any participants with an important protocol deviation. The PP population will be used to present sensitivity analyses for the primary and key secondary efficacy endpoints.
Safety Population	All randomized participants who receive at least one dose of study treatment. Participants will be analyzed according to the treatment they actually received. The Safety Population will be used for all safety summaries.
Pharmacokinetic (PK) Population	All participants in the MITT Population for whom a pharmacokinetic sample was obtained and analyzed. The PK population will be used for all PK summaries.

In the event one or more investigators are withdrawn from the trial due to concerns over protocol deviations, then a further population will be defined, which will consist of all participants in the MITT population excluding participants from those investigators. This population will be used to perform additional sensitivity analysis for the primary and key secondary efficacy endpoints.

10.3. Statistical Analyses

10.3.1. Efficacy Analyses

Endpoint	Statistical Analysis Methods
Primary	The primary efficacy endpoint is the change from baseline in trough and post-bronchodilator Clinic Visit FEV ₁ at Day 84. The primary intent will be to analyze this data by fitting a Bayesian dose response model. The 4-parameter Emax model will be fitted by first intent; however, should the data not allow for a suitable model fit, then other models may be attempted such

Endpoint	Statistical Analysis Methods
	
as the 3-parameter Emax, Log-linear model or similar.
 
The primary model will take the form:
 $\text{Change from baseline FEV}_1 = E_0 + (E_{\text{max}} * \text{Dose}^\gamma) / (ED_{50}^\gamma + \text{Dose}^\gamma)$ 
Where: E0 = the response at dose = 0 (placebo)
 
Emax = the maximal response
 
ED50 = the dose that yields 50% of the maximal response
 
γ = the slope parameter
 
Non-informative prior distributions will be fitted to all modeling parameters, ensuring that they are non-informative within the parameter space. Functional uniform priors will be attempted to be fitted by first intent however other prior distributions may be considered. Full details of the specification of prior distributions will be documented in the RAP.
 
The posterior mean change from baseline, along with 95% Credible Intervals, will be presented for each of the studied doses along with the placebo corrected results obtained from the non-linear model. Graphical representation of the dose response across the full dose range will also be produced to allow inference to be made for the non-studied doses based upon the model fit. Posterior probabilities that the true improvement is greater than 0 mL, 50 mL and 100 mL will also be presented.
 
Full details of the statistical analysis will be documented in the RAP.

Secondary	
The key secondary endpoint of number of exacerbations (moderate and severe) over the 12-Week treatment period will be analysed using a Bayesian generalized linear model assuming a negative binomial distribution for the underlying exacerbation rate with a log link and an offset to account for the length of time in study for each participant. Non-informative priors will be used for all modelling assumptions. The exacerbation rates for the selected nemiralisib dose and placebo arms, along with the ratio in exacerbation rates nemiralisib/placebo, will be estimated and corresponding 95% credible intervals produced.

Exploratory	Will be described in the RAP

10.3.2. Safety Analyses

Safety endpoints will be summarized by treatment group and all safety analyses will be performed on the Safety Population. Further details will be described in the RAP.

10.3.3. Population PK

A population non-linear mixed effects analysis or other appropriate method(s) will be performed on the sparse plasma samples using an optimal population PK model to describe the time course of systemic exposure of nemiralisib in this target subject population and associated inter- and residual variability. A covariate analysis will be undertaken to evaluate any subject factors (including demographic, physiological, co-medication, pharmacogenetic markers) likely to influence the systemic exposure to nemiralisib in this participant population. Appropriate validation of this population analysis will be performed in line with the European and US regulatory guidance documents on population PK analysis [EMA- [CHMP/EWP/185990/06](#), 2008 and the [FDA](#), 1999]. Full details of analysis will be provided in the RAP.

10.3.4. Pharmacokinetic/Pharmacodynamic Analyses

A longitudinal population dose- FEV_1 response analysis will be undertaken using trough FEV_1 at all measured time points over the duration of the study. Quantification of dose-response relationship, covariate effects, and time courses such as placebo effect onset, disease progression, and dose-related effect onset and offset will be characterized if data are amenable. This analysis may provide additional support for dose selection in future studies.

In addition, an exposure-driven clinical safety analysis will be performed using participant-specific exposure data and corresponding systemic safety signals, if data allow. If data are amenable, any relationship between steady state individual average drug levels (C_{ss}) with corresponding PROs will be assessed.

The above analysis will be conducted in alignment with the FDA and ICH E4 guidance documents [FDA Guidance for Industry. Exposure-Response relationships- Study Design, Data Analysis, and Regulatory Applications. FDA, Rockville, MD, April 2003 ([FDA](#), 2003), Dose Response Information to Support Drug Registration- [ICH E4](#), 1994]. Full details of analysis will be provided in the Reporting and Analysis Plan (RAP).

10.3.5. Interim Analyses

Interim analyses will be performed during the course of the study.

Interim analyses of the primary endpoint of change from baseline in clinic visit FEV_1 at Day 84 will be performed to determine whether or not any adjustments to the randomization ratio across the nemiralisib doses would help optimize the characterization of the dose response profile. Adjustments could include starting randomization to a nemiralisib dose of 25 mcg QD and/or ceasing randomization to an existing dose(s) of nemiralisib and/or modification of the allocation ratios for the existing nemiralisib doses. Change from baseline in clinic visit FEV_1 will be analyzed by fitting a Bayesian E_{max} dose response model, as described in Section 10.3.1. The timing of interim analyses of FEV_1 will be pre-specified in the RAP, prior to any unblinding taking place.

In addition, interim analyses will be used to assess the study for futility, to amend the stratification proportions by index exacerbation severity status (moderate or severe) and

to assess the study endpoint assumptions made prior to the study. The specific details regarding the interim analyses will be documented, prior to any un-blinding taking place, in the RAP. The timing of these analyses will depend upon recruitment and may be performed at the same time as the interim analyses of change from baseline FEV₁.

Additionally, an unblinded interim analysis will be conducted at the end of the 12-week treatment period to inform internal program-related decision making.

All interim analyses will be based on un-blinded data and will be performed by the study statistics and programming team (see Section 7.4). The randomization schedules and unblinded datasets will be stored on internal restricted drives. The GSK study team, with the exception of the statistics and programming team, will not have access to an un-blinded copy of the randomization schedule during the course of the trial.

The full details of the interim analyses will be pre-defined in the RAP.

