7.3. Method of Treatment Assignment

All participants will be centrally randomized using an Interactive Response Technology (IRT). Before the study is initiated, the log-in information and directions for the IRT will be provided to each site.

A centrally randomised schedule will be utilized to randomize participants into one of the seven treatment arms. Participants will be stratified by severity of the index exacerbation (moderate or severe) and whether or not the participant will provide PK samples. If required, additional schedules will be created for each change to the randomization ratios.

Study treatment will be dispensed at the study visits summarized in the SoA.

Returned study treatment should not be dispensed to the participants.

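### The printed one-intercept Emax model can bias dose estimates if doses are opened, closed or re-weighted mid-study and mean response differs between stages

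*Protocol*

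**What the plan says.** Section 10.3.5 lists what interim analyses of Day 84 FEV1 may do to allocation: "Adjustments could include starting randomization to a nemiralisib dose of 25 mcg QD and/or ceasing randomization to an existing dose(s) of nemiralisib", and also "modification of the allocation ratios for the existing nemiralisib doses". Interims may further be used "to amend the stratification proportions by index exacerbation severity status (moderate or severe"), possibly at the same time as the FEV1 interims. Section 7.2 separately allows the safety review committee's findings to halt an arm and move its allocation to other arms. The notes at the end of section 2 say that adding 25 mcg would not require a protocol amendment.

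For the analysis, 10.3.1 states "The primary model will take the form" and prints a four-parameter Emax curve with one E0, one Emax, one ED50 and one slope. No stage, severity or PK-subgroup term appears. Section 10.3.5 says the interim FEV1 data "will be analyzed by fitting a Bayesian E_{max} dose response model, as described in Section 10.3.1". Section 10.3.1 also says "Full details of the statistical analysis will be documented in the RAP".

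Randomization is stratified by index severity and PK subgroup (section 10.1). Section 7.3 makes each stage identifiable: "If required, additional schedules will be created for each change to the randomization ratios".

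**The concern.** While allocation is constant, every arm is spread over the study in the same way as placebo, so any drift in mean response cancels in each comparison with placebo. A dose-specific change breaks this. A dose opened later is observed only in later participants and a closed dose only in earlier ones, while placebo, if its share is kept, is observed in both. A single E0 compares each arm with the average placebo participant over the whole study, so a between-stage difference in mean FEV1 change goes partly into the dose effect.

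Such a difference could come from calendar drift. It could also come from the sponsor, if the severity mix is amended at the same interim as the ratios. Sections 5.4 and 5.5 make this curve the basis for choosing the minimal effective dose for later studies, so errors at opened or closed doses bear directly on that choice.

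**Working it through.** **Inputs from the protocol.** 1,250 randomized, 20% withdrawal, 1,000 completers (10.1). SD 300 mL at both time points with correlation 0.7 (10.1.1). Success is a posterior probability above 90% that any dose beats placebo (10.1.1).

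**Reproducing Table 2.** With weights 3:1:1:1:1:1:3 (sum 11), placebo and 750 mcg get 1,250 × 3/11 = 340.9 and each other dose 1,250/11 = 113.6. Completers are 0.8 times these, 272.7 and 90.9. Table 2 gives 340, 114, 272 and 91, so it reproduces. The printed ratio has six terms for seven arms, but Table 2 matches the seven-term version.

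**Assumed, not in the protocol.** Half of completers precede the change; the stage shift m is 0, ±20 or ±40 mL; and the allocation patterns are those below. As one illustration of m, a 20-point change in the severe share with an assumed 100 mL severe-moderate gap gives 0.20 × 100 = 20 mL.

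**Raw bias against pooled placebo.** Bias = m × (later-stage share of the arm − later-stage share of placebo).

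- No ratio change: shares are equal, so bias is 0 for any m. This covers a severity-mix change on its own.
- 25 mcg merely added (later weights sum to 12): placebo has 500 × 3/11 = 136.4 early and 500 × 3/12 = 125 late, a later share of 125/261.4 = 0.48. Bias for 25 mcg is 0.52m, or 10.4 mL at m = 20; for the other doses it is 0.
- 100, 250 and 500 mcg closed, 25 mcg opened, each low dose at weight 5/3: +0.50m for 25 mcg, −0.50m for each closed dose, (5/3)/(8/3) − 0.5 = +0.125m for 12.5 and 50 mcg, and 0 for 750 mcg.
- 250, 500 and 750 mcg closed, 25 mcg opened, 12.5 to 100 mcg at weight 2: −0.50m for each closed dose, +0.50m for 25 mcg, and 2/3 − 1/2 = +0.17m for 12.5, 50 and 100 mcg.

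**Effect on the fitted curve.** SD of change = 300 × √(2 × (1 − 0.7)) = 232.4 mL. I used a flat true dose response, 1,000 completers, and 3,000 simulated three-parameter frequentist Emax fits per case, as the protocol did for its own simulations. False success is a fit that meets the success rule for any dose. The Monte Carlo standard error near 18% is √(0.18 × 0.82/3,000) = 0.7 points.

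| Change halfway | Intercept | False success at m = 0 / −20 / +20 | Mean error at 750 mcg, m = −20 / +20 (mL) |
|---|---|---|---|
| None | one | 17.5 / 17.3 / 17.0% | −0.1 / −0.2 |
| None | per stage | 18.0 / 17.2 / 18.7% | −0.2 / +0.8 |
| 25 added | one | 18.2 / 19.4 / 17.6% | +0.6 / −0.5 |
| 25 added | per stage | 18.8 / 17.1 / 17.1% | 0.0 / −0.5 |
| 100/250/500 closed, 25 opened | one | 19.5 / 22.6 / 15.3% | +3.5 / −3.3 |
| 100/250/500 closed, 25 opened | per stage | 17.7 / 18.7 / 19.2% | +0.4 / +0.2 |
| 250/500/750 closed, 25 opened | one | 19.7 / 33.1 / 11.5% | +11.3 / −12.8 |
| 250/500/750 closed, 25 opened | per stage | 19.0 / 18.4 / 17.4% | 0.0 / −1.1 |

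In the last pattern at ±40 mL (400 runs), one intercept gave 55% at −40 and 7.5% at +40, with errors of about ±25 mL at 750 mcg.

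When 25 mcg was merely added, the fitted 25 mcg effect averaged only −0.5 and +0.2 mL at m = −20 and +20, although the raw contrast carries about 10 mL: neighbouring doses hold the curve in place. The distortion is largest when several high doses close, because those doses together determine the upper end.

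**The case against.** The strongest reply is that 10.3.1 prints only the structural curve and leaves full details to the RAP, which is not shown and where covariates normally sit. It stands to this extent: the absence of stage and severity terms is established for the printed equation only. It does not dispose of the point, because the protocol commits to that form and carries it into the interims while permitting the changes that make one intercept unsafe.

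A reader might infer that dose is necessarily confounded with stage and severity. The documents do not support that. Every adaptation is optional, and bias needs both a dose-specific allocation change and a between-stage difference in mean response. Amending the severity mix alone shifts all concurrently randomized arms alike under stratified randomization.

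A reader might also take half the stage shift as the error in the planned 25 mcg estimate. That figure is a raw contrast, and the fits above show it barely reaches the curve when 25 mcg is simply added. The 33% result needs 750 mcg to close, which 10.3.5 does not exclude but which is less likely for the dose planned for the exacerbation comparison.

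Nor is bias shown for the exacerbation comparison: if 750 mcg and placebo keep constant shares throughout, it is unaffected.

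Finally, the longitudinal dose-FEV1 analysis in 10.3.4 does consider covariate effects. It is supportive, depends on the data being amenable, and does not name stage.

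**Conclusion.** The point holds conditionally. If allocation changes for particular doses and mean FEV1 change differs between stages, the printed model can bias dose estimates. The raw bias is about half the shift for an arm opened or closed midway: about 10 mL for 20 mL, and 0 without a shift or a ratio change. For scale, 10.1.1 uses 25 mL for a non-efficacious difference and 75 mL for a minimum clinically meaningful one; neither is a decision bound for 25 mcg.

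On the fitted curve the effect runs from negligible (25 mcg merely added) to material (several high doses closed), and it can raise or lower the chance of declaring success. The shift, its timing and the allocation patterns are assumptions, and the four-parameter Bayesian model was not run.

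A reader might suspect that 12.5 mcg, added by Amendment 02, already has this problem. The document does not say whether anyone was randomized before that change, so this is not claimed.

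**What to change.** In 10.3.1 and 10.3.5, state that:

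- the Emax model includes index severity, which is already a randomization stratum;
- once any allocation change has been made, the model has a stage-specific intercept, with stage defined by the randomization schedule version, at later interims and at the final analysis;
- any dose opened or closed mid-study also gets a sensitivity analysis against concurrently randomized placebo only.

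Add a stage term to the exacerbation model only if the share of the selected dose or of placebo changes between stages.

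The cost is wording and one or two degrees of freedom. Stage can be read from the schedules described in 7.3, so no new data are needed. With no ratio change, false success was about 17% to 19% with or without the stage term.

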12. APPENDICES

12.1. Appendix 1: Abbreviations and Trademarks

Abbreviations

AB	Antibiotic
AE	Adverse Event
ALT	Alanine Aminotransferase
APDS	Activated Phosphoinositide 3-kinase Delta Syndrome, also referred to as p110delta-Activating mutation causing senescent T cells, Lymphadenopathy and Immunodeficiency (PASLI)
AST	Aspartate Aminotransferase
ATS	American Thoracic Society
AUC	Area Under the Plasma Drug Concentration versus Time Curve
BIB	Bioanalysis, Immunogenicity, Biomarkers
BMI	Body Mass Index
BP	Blood Pressure
BUN	Blood Urea Nitrogen
CAT	COPD Assessment Test
CXCL10	Chemokine interferon- γ inducible protein 10 kDa
CFR	Code of Federal Regulations
CIOMS	Council for International Organizations of Medical Sciences
C _{max}	Maximum Observed Plasma Drug Concentration
CONSORT	Consolidated Standards of Reporting Trials
COPD	Chronic Obstructive Pulmonary Disease
CPAP	Continuous Positive Airway Pressure
CRF	Case Report Form
cRNA	Complimentary Ribonucleic Acid
CSR	Clinical Study Report
CT	Computed Tomography
CV	Cardiovascular
DRE	Disease Related Event
EC	Ethics Committee
ECG	Electrocardiogram
eCRF	Electronic Case Report Form
E-RS: COPD	Evaluating Respiratory Symptoms in COPD
ERS	European Respiratory Society
EU	European Union
EXACT-PRO	EXacerbations of Chronic Pulmonary Disease Tool – Patient-Reported Outcome
FDA	Food and Drug Administration
FEV ₁	Forced Expiratory Volume in One Second
FRC	Functional Residual Capacity

FRI	Functional Respiratory Imaging
FSH	Follicle Stimulating Hormone
FVC	Forced Vital Capacity
GCP	Good Clinical Practice
GCSP	Global Clinical Safety and Pharmacovigilance
GGT	Gamma Glutamyl Transferase
GSK	GlaxoSmithKline
HBcAb	Hepatitis B core antibody
HBsAg	Hepatitis B Surface Antigen
hcCRP	High-Sensitivity C-Reactive Protein
HCRU	Health Care Resource Utilization
HPLC	High-Performance Liquid Chromatography
HRT	Hormonal Replacement Therapy
IB	Investigator's Brochure
ICF	Informed Consent Form
ICH	International Conference on Harmonisation
IEC	Independent Ethics Committee
Ig	Immunoglobulin
IgG	Immunoglobulin G
IgM	Immunoglobulin M
IL-1	Interleukin-1
IND	Investigational New Drug Application
INR	International Normalized Ratio
IRB	Institutional Review Board
IRT	Interactive Response Technology
iSRC	Internal Safety Review Committee
IUD	Intrauterine Device
IUS	Intrauterine Hormone-Releasing System
Kg	Kilogram
Kg/m ²	Kilogram/square meter
LTOT	Long-Term Oxygen Therapy
mcg	Microgram
MDI	Metered-Dose Inhaler
MedDRA	Medical Dictionary for Regulatory Activities
MgST	Magnesium Stearate
mL	Milliter
MITT	Modified Intent to Treat
MSDS	Material Safety Data Sheet
NIPPV	Non-Invasive Positive Pressure Ventilation
OCS	Oral Corticosteroid
PI3Kd	Phosphoinositide 3-Kinase Delta
PGx	Pharmacogenetics
PK	Pharmacokinetic
PP	Per Protocol
PRO	Patient-Reported Outcome
QD	Once daily

QTc	Corrected QT Interval
QTcF	QT interval corrected for heart rate according to Fridericia's formula
RAP	Reporting and Analysis Plan
SAE	Serious Adverse Event
SCS	Systemic Corticosteroid
SDA	Source Document Agreement
SGOT	Serum Glutamic-Oxaloacetic Transaminase
SGPT	Serum Glutamic-Pyruvic Transaminase
siVaw	Specific Imaging Airway Volume
siRaw	Specific imaging Airway Resistance
SoA	Schedule of Activities
SoC	Standard of Care (in this protocol this refers to SoC for the index lesion)
SGRQ-C	St. George's Respiratory Questionnaire for COPD Patients
SRDP	Study Results Dissemination Plan
SRM	Study Reference Manual
SRT	Safety Review Team
SUSAR	Suspected Unexpected Serious Adverse Reaction
T _{1/2}	Terminal half-life
TLC	Total Lung Capacity
Tmax	Time at Maximum Plasma Concentration
TNF	Tumor Necrosis Factor
TPR	Third Party Resourcing
ULN	Upper Limit of Normal
US	United States of America
WBC	White Blood Cell
WHO	World Health Organization
WOCBP	Women of Childbearing Potential

Trademark Information

Trademarks of the GlaxoSmithKline group of companies
COPD Assessment Test (CAT)
DISKUS
ELLIPTA

Trademarks not owned by the GlaxoSmithKline group of companies
E-RS: COPD
EXACT-PRO
Propeller Sensor
SAS
SGRQ-C

12.2. Appendix 2: Clinical Laboratory Tests

- The tests detailed in [Table 6](#) will be performed by the central laboratory (Q2 Solutions) for all time points as shown in the SoA (Section 2).
- At Screening, for prompt assessment of the participant's eligibility local laboratory samples, with the exception of Hepatitis B, C and HIV, should be taken and the results received and reviewed prior to randomisation to allow for review of exclusion 18. It is important that a sample for analysis by the central laboratory is obtained at the same time and promptly sent to the central laboratory. The local lab results will not be entered into the CRF; however, they will be filed in the respective participant's source documentation
- Protocol-specific requirements for inclusion or exclusion of participants are detailed in Section 6 of the protocol.
- Additional tests may be performed at any time during the study as determined necessary by the investigator or required by local regulations.

Table 6 Protocol-Required Safety Laboratory Assessments

Laboratory Assessments	Parameters			
Hematology	Platelet Count RBC Count Hemoglobin Hematocrit	RBC Indices: MCV MCH %Reticulocytes	WBC count with Differential: Neutrophils Lymphocytes Monocytes Eosinophils Basophils	
Clinical Chemistry ¹	BUN	Potassium	Aspartate Aminotransferase (AST)/ Serum Glutamic-Oxaloacetic Transaminase (SGOT)	Total and direct bilirubin
	Creatinine	Sodium	Alanine Aminotransferase (ALT)/ Serum Glutamic-Pyruvic Transaminase (SGPT)	Total Protein
	Glucose (nonfasting)	Calcium	Alkaline phosphatase	Albumin
Other Screening Tests	
 • Follicle-stimulating hormone and estradiol (as needed in women of non-childbearing potential only) • Serum human chorionic gonadotropin (hCG) pregnancy test (as needed for women of childbearing potential)² at Screening and to confirm any positive 			

Laboratory Assessments	Parameters
	urine pregnancy test 
 • Urine pregnancy test (as needed for women of childbearing potential) at visits as shown in the SoA • Hepatitis B surface antigen [HBsAg] and hepatitis C virus antibody ³ • HIV antibody ³ The results of each local laboratory test will not be entered into the CRF; however, they will be filed in the respective participant's source documentation.

NOTES :

1. Details of liver chemistry stopping criteria and required actions and follow-up assessments after liver stopping or monitoring event are given in Section 8.1.1 and Appendix 7 All events of ALT $\geq 3 \times$ upper limit of normal (ULN) and bilirubin $\geq 2 \times$ ULN (>35% direct bilirubin) or ALT $\geq 3 \times$ ULN and international normalized ratio (INR) >1.5, if INR measured, which may indicate severe liver injury (possible Hy's Law), must be reported as an SAE (excluding studies of hepatic impairment or cirrhosis).
2. Serum testing
3. Hepatitis B surface antigen [HBsAg], hepatitis C virus antibody and HIV antibody will be assessed by the central laboratory only and will not be assessed at the local lab.

Laboratory/analyte results for the PK and biomarker analyses that could unblind the study will not be reported to investigative sites or other blinded personnel until the study has been unblinded.

